Any children not falling into any of these categories will be excluded from the analysis.

Definitions

1. Simple cases

Children presenting with SA or OM for the first time, and with no chronic comorbidities. Specifically:

- No orthopaedic surgery 6 months prior to presentation on same limb/joint
- No chronic co-morbidities (sickle cell disease, known immunocompromise, indwelling central venous catheter or PICC, cystic fibrosis, or cerebral palsy).

2. Complex cases

Children presenting with SA or OM who already have a diagnosis of SA or OM and/or have chronic comorbidities, but who are not presenting because of an infected implant from previous orthopaedic surgery. Specifically:

- Not presenting because of an infected implant
- Any orthopaedic surgery in 6 months prior to presentation on same limb/joint
- Any chronic co-morbidities (sickle cell disease, known immunocompromise, indwelling central venous catheter or PICC, cystic fibrosis, or cerebral palsy).

3. Infected implants

Children presenting with SA or OM who already have a diagnosis of SA or OM and who are presenting because of an infected implant from previous orthopaedic surgery.

4. Incorrect diagnosis of SA/OM

Some children captured by the database were treated for SA/OM but were later found to have a different diagnosis.

Completeness of follow-up

Follow-up data are collected at a follow-up visit at around 3 months post discharge. The number lost to follow up will be reported and the reasons where known will be documented. Any deaths and their causes will be reported separately.

Study Outcomes

This study examines many measurements routinely made in the diagnosis, treatment, and aftercare of children with SA or OM. There are three areas of key interest: Diagnosis (Objective 1); Treatment (Objective 2); and Complications Arising and/or Treatment Failures (Objective 3). The key endpoints are:

Diagnosis:

- Bones and joints affected
- Time taken from first presentation to:
 1. Referral to hospital
 2. Having surgery
 3. Initiation of IV antibiotics [this time-point used also as a proxy for a diagnosis being made]
- Surgical procedures carried out prior to diagnosis
- Imaging types used (X-ray, CT scan, ultrasound, bone scan, MRI), and results obtained
- Diagnostic blood tests carried out (Hb, WBC, N, Plt, CRP, ESR) and their outcomes
- Microbiological tests carried out (presence of any of 8 named micro-organisms)

Antibiotic Treatment in and post hospital stay:

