- Length of time on IV antibiotics
- Length of time on oral antibiotics
- Total length of time on antibiotics
- Length of time from presentation to discharge
- Blood tests carried out and their results
- Antibiotics prescribed (during hospital stay and at discharge)
- Dosage (Normal / High as defined in Children's British National Formulary)
- Adherence to discharge prescription
- Reasons for non-adherence or changes to prescribed regimes.

Complications / Failure of treatment

- Complication types
- Actions arising from complications
- Treatment failure (Y/N)

Analysis

The primary interest are the sub-group of children with acute SA / OM and no chronic comorbidities (simple cases). All analyses described below will therefore be carried out for this sub-group in the first instance. The other two sub-groups (chronic SA/OM and infections arising from previous orthopaedic surgery) will be analysed separately as a secondary analysis. See *Appendix A: Template Results Tables* for tables referred to in the following analysis plan.

Objective 1

- [1A] See Section 8.2 above for demography and definition of diagnosis groups. Numbers and percentages will be calculated and results tabulated separately for: demographics; diagnosis groups; presentation; history of orthopaedic surgery; medical history; and antibiotics prescribed prior to presentation. See Tables 1A-1,2,3,4,5,6 below
- [1B] The clinical time-line from first presentation through to diagnosis will be explored. Time to hospital referral, first imaging, surgery, radiological diagnosis, and initiation of IV antibiotics will all be summarised using appropriate descriptive statistics [see Table 1B-1].
- [1C] The number and percentage of cases undergoing different types of surgery prior to diagnosis will be reported [see Table 1C-1].
- [1D] The number and percentage of cases testing positive for at least one micro-organism, and each of 8 unique micro-organisms will be reported, split by centre type (Tertiary / Secondary). Any other micro-organisms detected will be categorised and reported as “Other”. Of cultures testing positive for *Staphylococcus aureus*, the number and percentage where PVL is tested for will be reported. The number and percentage of cases where a PCR test is also carried out will be calculated by centre type. [See Table 1D-1].

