The number and percentage of types of sample for micro-biological testing (e.g. blood, pus, etc.) that are typically taken from children will be reported [see Table 1D-2].
- [1E] The number and percentage of cases with test results at presentation for: each of 6 blood tests; and the combinations ‘CRP & ESR’ and ‘CRP & no ESR’ will be reported, split by centre type (Tertiary / Secondary) [see Table 1E-1]. A boxplot for each of the six blood test measures at presentation will be created to show the distribution of results. Proportions with elevated results (above centre-specific normal ranges) will be calculated for each blood test type [see Table 1E-2].

The blood test result ‘CRP_{max}’ will be summarised for culture-positive and culture negative cases and a box plot created to compare these. This analysis will be split by age-group. This is to explore whether a higher CRP_{max} is associated with particular organisms. Differences that are clinically significant will be tested for statistical significance using appropriate hypothesis tests [see Table 1E-3].
- [1F] There are five imaging methods that could be requested by clinicians to aid diagnosis. The number and percentage of cases for each imaging type used prior to diagnosis will be reported, split by centre type (Tertiary / Secondary) and of these the number and percentage abnormal [see Table 1F-1].

Objective 2

Treatment of children with SA or OM takes the form of antibiotic treatment and additionally for some cases, surgical intervention. Initially antibiotics are given intravenously. At a later date, antibiotics are given orally – the timing of the switch is based on clinical judgement that the child has recovered sufficiently and is capable of taking drugs orally.

- [2A] The lengths of time on IV antibiotics, oral antibiotics, and total antibiotic duration will be summarised using appropriate descriptive statistics. (Note that these times are based on what happened during hospital stay and what was **planned** at discharge. It is not possible to obtain data for the actual date when antibiotics were stopped post discharge.) Results will also be split by centre type, whether there was at least one surgical procedure after initiation of IV antibiotics, if CRP_{max} occurred at presentation, and by microbes detected. [See Table 2A-1].

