Other

Infection History in the last 12
calendar months?

Pneumonia

Septicaemia

Pyelonephritis

Cellulitis / soft tissue infection

Meningitis

Osteoarticular infection

Abdominal sepsis

Varicella

Other

History of Trauma in the last
month?

Other Surgery in 12 months prior to
presentation?

Pre-presentation variables that affect drug choice, dosage and duration. (Simple cases only)

TABLE 1A-7

Antibiotic Medical History	N(%)	Route		Duration
		IV	Oral	> 1 week
Penicillin allergy		-	-	-

Antibiotics (1 month
pre-presentation)

Any

Flucloxacillin

Clindamycin

Cefuroxime

Ceftriaxone

Amoxicillin

Co-Amoxiclav

Rifampicin

Vancomycin

Fusidic Acid

Teicoplanin

Other

1B: The clinical time-line for diagnosis

TABLE 1B-1

Diagnostic and hospital stay Time-line (Days)	Appropriate Summary Statistics
From first presentation to:	
Hospital Referral	
1 st Imaging	
Pre-diagnosis surgery	
Radiological diagnosis	
Initiation of IV antibiotics	
(proxy for diagnosis of OM/SA)	

1C: Surgical procedures carried out post presentation and prior to diagnosis (before or on the same day as initiation of IV antibiotics).

TABLE 1C-1

Surgery types	Rate n (%)
Any	
Aspiration	
Incision and drainage	
Drill decompression	
Curettage/excision	
Arthrotomy	
Arthroscopy	
Amputation	

Debridement

Fasciotomy

Compartment decompression

Secondary closure

Skin graft

Other plastic surgery

1D: Summary of range of tests carried out and sensitivity of conventional microbiological tests. (Simple cases only)

TABLE 1D-1

N(%)
Children with at least one conventional test carried out
At least one micro-organism detected
Specific mirco-organisms detected by conventional testing:
Staphylococcus Aureus
PVL tested for?
Kingella Kingae
Streptococcus pyogenes
Pseudomonas
Group b Streptococcus
Salmonella
Candida
Tuberculosis
Other
PCR testing carried out

Types of sample used for conventional microbiological testing. (Simple cases only)

TABLE 1D-2

N(%)

Number of different
sample types taken

0

1

2

>2

Sample types. Children
that had at least one:

Pus (periosteal)

Bone biopsy

Pus/Wound swab

Joint aspirate

Other

1E: Blood-tests carried out at presentation. (Simple cases only)

TABLE 1E-1

Blood tests at presentation	N(%) with at least one measurement on day of presentation	Summary statistic for test results	% with elevated* results
Hb			
WCC			
N			
Plt			
CRP			
ESR			
CRP & ESR		-	-
CRP & not ESR		-	-
CRP _{max} occurring at presentation		-	-

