*Above the centre specific normal range

1F: Comparing average CRP_{max} for each culture negative vs. positive, by age-group. (PCR and conventional test results combined; Simple cases only).

TABLE 1F-1

Microbe	Summary statistics for CRP _{max}					
	< 1 year		1-6 years		6-16 years	
	+ve	-ve	+ve	-ve	+ve	-ve
Staphylococcus Aureus						
Kingella Kingae						
Streptococcus pyogenes						
Pseudomonas						
Group b Streptococcus						
Salmonella						
Candida						
Tuberculosis						
Other						

1G: Imaging types routinely used to aid diagnosis (On day of or prior to initiation of IV; Simple cases only).

TABLE 1G-1

Imaging Type	N(%) with at least one image	Number (%) Abnormal
X-ray		
CT scan		
Ultrasound		
MRI		
Bonescan		

What is the range of durations of intravenous and oral antibiotics used to treat osteomyelitis?

2A: The clinical time-line for antibiotic treatment.

TABLE 2A-1

Antibiotic Treatment Time-line (Days)	Appropriate Summary Statistics
Length of time on:	
IV	
Oral ^(a)	
Total ^(b)	

^(a)Use time on oral antibiotics pre-discharge plus planned duration, as proxy for actual duration.

^(b) Length of time treated with any antibiotic (for some children oral antibiotics were given concurrently to IV. So the Total length of time is not necessarily the time on IV plus the time on Oral)

Types of antibiotic regimes experienced.

TABLE 2A-2

Antibiotic Regime	All	Centre Type	
		Tertiary	Secondary
Number of different antibiotics given at initiation of treatment			
1			
2 or more			
Timing of oral switch			
Very Early (< 1 week)	Also report median & IQR		
Early (1-2 wks)	for each category		
Standard / Late (> 2 wks)	here		

Total course of antibiotics

Shortened (< 6 weeks)

Standard (> 6 weeks)

DoseAugmented at least once^(a)

Standard throughout

**Total number of antibiotics
prescribed****IV:**

1

2

>2

Oral:

1

2

>2

^(a)At least one IV antibiotic given at a high dose

2B: IV and oral antibiotics prescribed prior to discharge.

TABLE 2B-1

Antibiotic	Given at least once	Part of initial prescription	Daily dose per kg weight of child	Frequency					Duration (> 1 week)
				6 hourly	8 hourly	12 hourly	Once daily	Other	
IV									
Flucloxacillin									
Clindamycin									
Cefuroxime									
Ceftriaxone									
Other									
Oral									
Flucloxacillin									
Clindamycin									
Amoxicillin									
Co-Amoxiclav									
Rifampicin									

Other

TABLE 2B-2

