Complication type:						
Fever						
Recurrence of						
Infection						
Dislocation						
Subluxation						
Pathological						
Fracture						
Sinus						
Other						

3B: Treatment failures and complications by type of antibiotic regime.

TABLE 3B-1

Antibiotic Regime	Treatment Failure?			Any complication?		
	Yes	No	Odds ratio	Yes	No	Odds Ratio
Timing of oral switch						
Early (< 2 weeks)						
Standard / Late (> 2 wks)						
Total course of antibiotics						

Shortened (< 6 weeks)

Standard (> 6 weeks)

Dose Repeated for IV
and oral separately

High

Majority Lower range

3C: Treatment failures and complications by type of surgery.

TABLE 3C-1

Surgery	Treatment Failure?			Any complication?		
	Yes	No	Odds ratio	Yes	No	Odds Ratio
Surgery undertaken after date of 1 st presentation						
Aspiration						
Incision and drainage						
Drill decompression						
Curettage/excision						
Arthrotomy						
Arthroscopy						
Amputation						
Debridement						
Fasciotomy						
Compartment decompression						
Secondary closure						
Skin graft						
Other plastic surgery

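### Antibiotics taken in the month before presentation are listed as affecting duration, but are never related to duration in [2A] or allowed for in the [3B] odds ratios

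*SAP*

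**What the plan says.** Objective 2 asks for the range of IV and oral antibiotic durations and what influences them, giving surgery, blood tests and microbiology as examples.

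Appendix A, Table 1A-7, stands under the heading "Pre-presentation variables that affect drug choice, dosage and duration. (Simple cases only"). It lists penicillin allergy and any antibiotic taken in the month before presentation, by drug, by route (IV or oral) and by whether it lasted more than 1 week.

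Study Outcomes names "Total length of time on antibiotics" as a key endpoint, under the heading "Antibiotic Treatment in and post hospital stay". The note in [2A] fixes the basis of the IV, oral and total times: "these times are based on what happened during hospital stay and what was" planned at discharge. In Table 2A-1, footnote (a) on the oral row reads "Use time on oral antibiotics pre-discharge plus planned duration, as proxy for actual duration". Footnote (b) on the total row reads "Length of time treated with any antibiotic" and gives no start point.

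On splits, [2A] says "Results will also be split by centre type, whether there was at least one surgical procedure after initiation of IV antibiotics", and then adds whether the maximum CRP occurred at presentation and which microbes were found. Prior antibiotics are not in the list.

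[3B] and Table 3B-1 take the classes built from these times as exposures: oral switch before or after 2 weeks, and total course "Shortened (< 6 weeks") or longer. Odds ratios with 95% confidence intervals are planned for treatment failure and for any complication.

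**The concern.** The SAP names a variable as affecting duration, records it, and then does nothing with it where duration is analysed. Two things are at stake.

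The first is the SAP's own question. Objective 2 wants to know what drives duration, and the evaluation is meant to inform whether a trial of shorter IV treatment is feasible. A reader of Tables 1A-7 and 2A-1 will learn how many children had prior antibiotics and how long children were treated, but not whether the two are related.

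The second is the reading of Table 3B-1. Prior antibiotics could be related both to the length of course chosen and to the outcome, so they are a possible confounder of the crude odds ratios. Where the earlier antibiotics were for the same infection and led into the hospital course, the child's class would also understate the treatment received.

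**Working it through.** The SAP gives no rate, mean or standard deviation that bears on this point, so there is no figure to reproduce. The check sets the passages side by side and then asks what could follow.

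**1. Is prior treatment inside the durations?** No. The outcome heading limits them to treatment during and after the hospital stay, and the [2A] note says the same. Footnote (b) of Table 2A-1, read alone, could be taken to include earlier treatment, but the note in [2A] settles that it does not.

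**2. Is prior treatment related to duration anywhere?** No. [2A] has four splits: centre type, surgery after the start of IV, maximum CRP at presentation, and microbes. [3B] has three exposures: timing of oral switch, total course and dose. Neither section uses prior antibiotics to split, stratify or restrict.

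**3. Are the recorded prior drugs relevant?** Plausibly. Table 1A-7 contains all four named IV drugs of Table 2B-1 (flucloxacillin, clindamycin, cefuroxime, ceftriaxone) and all five named oral drugs (flucloxacillin, clindamycin, amoxicillin, co-amoxiclav, rifampicin). This overlap does not show that they were given for the bone or joint infection. As laid out, Table 1A-7 has no column for indication or dates.

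**4. Which children could change class?** Let T be the recorded total course in days and d the prior days. If prior days counted towards the course, a child would move from shortened to standard only if T < 42 and T + d ≥ 42, that is, 42 − d ≤ T < 42.

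| d (days) | T must be at least (42 − d) |
|---|---|
| 1 | 41 |
| 8 | 34 |
| 30 (about the whole look-back month) | 12 |

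Children with T below 42 − d, or at or above 42, keep their class whatever is decided about prior days.

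**5. How many might that be?** Two shares are needed and the SAP gives neither. Assume that 10-30% of cases had prior antibiotics and that 10-30% of those fall in the window. With the SAP's accrual estimate of at least 500 cases:

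- low: 500 × 0.10 × 0.10 = 5 children (1%)
- high: 500 × 0.30 × 0.30 = 45 children (9%)

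The 500 covers all diagnosis groups, so for the same shares the count among simple cases, which are analysed first, would be smaller. The range also treats all prior antibiotics as being for the same infection and as counting in full. It shows how the answer depends on the assumptions; it is not an estimate.

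**The case against.** The strongest reply is that the scope is stated openly. The endpoint is treatment in and after hospital, and it measures that. This stands: the durations are not too short against their own definition.

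A reader might go further and infer that part-treated children are misclassified, that is, filed as having shorter courses than they had. The document does not support that. Simple cases are by definition presenting with the disease for the first time, and the start of IV antibiotics is the SAP's proxy for diagnosis. Table 1A-7 shows neither indication nor dates, and gives length only as over 1 week or not. Nothing shows that the earlier drugs treated this infection or ran on into the hospital course, and the tabulated data would not allow days to be added to the total. Nor does anything suggest adding earlier IV days to the timing of the oral switch, which the SAP describes as a switch from the IV course begun as treatment.

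It can also be said that sub-objective 1A promises only to describe these variables and singles out age, allergies and co-morbidities, and that [2A] covers each of Objective 2's examples. That is fair, so no explicit commitment is broken. But the examples are only examples, and the heading of Table 1A-7 puts prior antibiotics among the variables that affect duration. Leaving that relation unexamined remains a gap, even in a descriptive study whose Table 3B-1 offers only an overview.

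**Conclusion.** The point holds in a limited form. Prior antibiotics are recorded and are presented as affecting duration, but they are not related to duration in [2A] and are disregarded when duration classes become exposures in [3B]. The stated durations are correct as defined.

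Some children may have had more treatment than their class shows, and the odds ratios may be confounded by prior treatment. The SAP does not allow either effect to be sized: the 5 to 45 children in 500 rest wholly on assumed shares. The case for the change does not depend on that range. Even if no child would cross a cut-off, the split helps to answer a question the SAP itself asks.

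**What to change.** 1. In [2A] and Table 2A-1, add a split by antibiotics in the month before presentation: none, 1 week or less, more than 1 week. The row for any antibiotic in Table 1A-7 is the natural basis. The Table 2A-1 template has a single results column, so the new split should be laid out with the four already promised in the text.
2. Repeat Table 3B-1 in children with no prior antibiotics, labelled as a sensitivity analysis.
3. Add to the footnotes of Table 2A-1 that all durations exclude antibiotics taken before presentation.

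No new data are needed. The cost is one more split and one repeated table with fewer cases: under the assumed 10-30% with prior antibiotics, 500 × 0.90 = 450 down to 500 × 0.70 = 350 of 500 children would remain, and fewer among simple cases, so the confidence intervals will tend to be wider. Some prior antibiotics will have been for another illness, which blurs the split. That is also why a split is preferable to adding prior days to the total.

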- 1B:** Describe the clinical time-line for diagnosis: summarising the number of days from presentation when key clinical actions (1st imaging, surgery and initiation of IV antibiotics) occur.
- 1C:** Describe the surgical procedures carried out prior to diagnosis.
- 1D:** Summarise the types of microbiological tests carried out and the types of samples taken. Specifically, find the proportion of centres that are performing PCR tests, and testing for Panton-Valentine Leukocidin producing *Staphylococcus aureus*.
Calculate the proportion of children testing positive for: at least one micro-organism; and each specific micro-organism (using conventional techniques, ie not PCR).
- 1E:** Describe the combinations of blood-tests carried out at presentation and summarise the test results. Find the proportion of children with elevated results for each blood-test type at presentation (results above centre-specific normal ranges), and the proportion of children with CRP_{max} occurring at presentation. Describe the types of samples.
- 1F:** Summarise CRP_{max} by age-group and micro-organisms detected.
- 1G:** Describe the imaging methods routinely used to aid diagnosis. What proportions of each method gave an abnormal result..
- 2A:** Describe the clinical time-line for antibiotic treatment (specifically when antibiotics are started) Describe the types of antibiotic regimes prescribed. Summarise the number of different antibiotics given as initial treatment, and the total number of different antibiotics patients receive over the durations of treatment by each route. Summarise the numbers of children being given different types of regime: early vs

normal length of time to oral switch; dosage – how many were given normal doses throughout; shortened vs standard length of time on antibiotics.

- 2B:** Describe the IV and oral antibiotics prescribed during hospital stay. For each antibiotic: which were prescribed at least once; which were part of the initial treatment; what was the average daily dose; with what frequency were doses given; and was the duration greater than 1 week. Were there differences in initial IV antibiotic prescriptions between secondary and tertiary site types; between children with and without penicillin allergy; and with and without sickle cell disease?

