Antibiotic regimes will be further summarised for the sample: Number of antibiotics given in the initial treatment; timing of oral switch (<1 wk, 1-2 wks and >2 wks)); total course of antibiotics (shortened vs standard); dose (augmented at least once vs standard dose throughout where ‘augmented at least once’ is defined as having at least one high dose of IV antibiotics); and total number of different antibiotics prescribed over the full treatment period [see Table 2A-2].

- [2B] Antibiotics prescribed during hospital stay will be summarised using frequencies and percentages. There are a large number of antibiotics that could be prescribed by either route. Of these, 4 named IV antibiotics and 5 named oral antibiotics are of particular interest. A category labelled ‘other’ will be used to define all other antibiotics given by each route. For each antibiotic and route, summary statistics will be reported for whether it was part of the initial prescription; given at least once; frequency of administration of doses during a day; daily dose per kg weight of child; and duration of course (> 1 week Y/N). This will give an overview of the most commonly prescribed antibiotics during hospital stay [see Table 2B-1].

Initial IV antibiotic prescriptions will be compared between secondary and tertiary site types; between children with and without penicillin allergy; and with and without sickle cell disease [see Table 2B-2].

- [2C] Blood test results are routinely used to aid the decision to stop giving antibiotics via IV (ie. oral switch). The combinations of blood tests carried out immediately prior to (on the day before or on the day of) the oral switch will be reported as numbers and percentages. CRP as a proportion of CRP_{max} will be summarised [see Table 2C-1].

The change in blood test results over time will be explored graphically using boxplots. For each blood test type, a plot will be produced showing the distribution of results at: presentation; initial of IV; and on each day following start of IV.

- [2D] The number and percentage of cases undergoing different types of surgery post diagnosis will be reported [see Table 2D-1].
- [2E] Appropriate summary statistics will be used to describe length of hospital stay for cases – overall, and split by age-group and centre type [see Table 2E-1].
- [2F] The number and percentage of cases with imaging after initiation of IV will be reported split by site type and image type, with results given.

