- [2G] Antibiotics prescribed at discharge will be summarised using frequencies and percentages. There are a large number of antibiotics that could be prescribed by either

route. Of these, 4 named IV antibiotics and 5 named oral antibiotics are of particular interest. A category labelled ‘other’ will be used to define all other antibiotics given by each route. For each antibiotic and route, summary statistics will be reported for whether it was given at least once; daily dose per kg weight of child; and planned duration of course. This will give an overview of the most commonly planned antibiotic regimes at discharge [see Table 2F-1].

[2H] Antibiotic regimes post discharge are not always adhered to. The number and percentage of those stopped early will be reported, split by who took the decision (Parent / Hospital / GP). In the same way the number and percentage of patients who had a change to the planned regime will be reported split by who made the change (Hospital / GP). The frequencies of 5 possible reasons for shortening or changing regime will be explored [see Table 2G-1].

Objective 3

[3A] The number and percentages of cases experiencing a complication of any kind will be reported. These will be further split by ‘Complication Type’, and cross-tabulated with ‘Action Taken’ (None / Surgery / Change of antibiotic regime / Re-admission to hospital / Other) [see Table 3A-1].

[3B] Treatment failure is determined by complications that result in certain actions. e.g. Surgery. The outcomes ‘Treatment Failure’ (Y/N) and ‘Any Complication’ (Y/N) will be cross-tabulated with three antibiotic regime variables: Timing of oral switch (Early / Standard); Total course of antibiotics (Shortened / Standard); and Overall dose (High / Normal). Associations between regime types and outcomes will be measured using odds-ratios and 95% CIs. This will give an overview of whether treatment failure and complications may be more likely for certain types of regime [see Table 3B-1].

[3C] Treatment Failure (Y/N) and Any Complication (Y/N) will be cross-tabulated with surgery undertaken (limited to surgery post presentation). Associations between surgery types and outcomes will be measured using odds-ratios and 95% CIs. This will give an overview of whether treatment failure and complications may be more likely for certain types of surgery [see Table 3C-1].

Analyses of missing data / withdrawals

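### Dose has only two levels and no rule for a dose below the formulary range, so such children fall by default into the standard-dose count in [2A] and apparently into the comparator in [3B]

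*SAP*

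**What the plan says.** Dose appears in five places in the SAP, always with two levels at most.

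- Study Objectives, 2A asks "how many were given normal doses throughout".
- Study Outcomes, under antibiotic treatment, lists "Dosage (Normal / High as defined in Children's British National Formulary".
- Analysis, Objective 2, [2A] sets out "dose (augmented at least once vs standard dose throughout where" the augmented category "is defined as having at least one high dose of IV antibiotics". The standard category has no definition of its own. Table 2A-2 has the same two rows, and its footnote also restricts the augmented row to IV antibiotics.
- Analysis, Objective 3, [3B] cross-tabulates treatment failure and any complication with "Overall dose (High / Normal" and measures the association by odds ratios with 95% CIs. No reference level is named.
- Appendix A, Table 3B-1 has the rows *High* and *Majority Lower range*, to be repeated for IV and oral separately.

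Separately, [2B] and [2G], with Tables 2B-1 and 2G-1, summarise daily dose per kg by antibiotic and route, in hospital and at discharge. These summaries are not compared with the formulary range or related to outcome.

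**The concern.** A child who has had no high IV dose has not necessarily had normal doses throughout. With two rows and one definition, the second row is whatever the first leaves over. That remainder includes children dosed below range. It also includes children whose only high dose was oral, because the [2A] definition covers IV alone. The row is then read as the answer to sub-objective 2A, which it is not.

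For [3B], the stake is the meaning of the odds ratio. If the comparator pools in-range and below-range dosing, and below-range children fail more often, high dosing looks protective even where it does not differ from in-range dosing. [3B] is meant to show whether failure may be more likely under certain regimes, and the evaluation as a whole feeds a decision about a future trial.

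**Working it through.** The SAP states no figure on this point, so there is nothing to reproduce. The check has two parts.

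**1. Where does a below-range dose go?**

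| Place | One side | Other side | Rule given | Route |
|---|---|---|---|---|
| Study Outcomes | High | Normal | by formulary | not stated |
| [2A], Table 2A-2 | augmented at least once | standard throughout | first side only: one high dose suffices | IV only |
| [3B] text | High | Normal | none | not stated |
| Table 3B-1 | High | Majority Lower range | none beyond the label | IV and oral separately |

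No row of this table has a place for below range. In [2A] the allocation follows by complement: no high IV dose means standard throughout. In [3B] the comparator has no stated lower bound, so below-range children have no other visible place. However, the majority wording and the split by route mean that the [3B] variable cannot be assumed to be the [2A] variable.

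**2. How much could it matter?** All inputs are assumptions, because the SAP gives no failure rate, below-range share or relative risk. Take:

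- failure risk 5% on both high and in-range doses, so the true odds ratio is 1;
- f = share of the comparator that is below range;
- p = failure risk in that share;
- all below-range children in the comparator.

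Comparator risk: r = (1 − f) × 5% + f × p. Observed OR = (0.05/0.95) ÷ (r/(1 − r)).

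| f | p | r | Observed OR |
|---|---|---|---|
| 5% | 10% | 4.75% + 0.50% = 5.25% | 0.0526/0.0554 = 0.95 |
| 10% | 15% | 4.50% + 1.50% = 6.00% | 0.0526/0.0638 = 0.82 |
| 20% | 15% | 4.00% + 3.00% = 7.00% | 0.0526/0.0753 = 0.70 |

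Over a wider grid (f from 5% to 30%, below-range risk 1.5 to 3 times the in-range risk) the observed OR runs from 0.97 to 0.61 at a 5% base risk and from 0.97 to 0.58 at a 10% base risk. Separating the below-range children returns it to 1.

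For the [2A] count, if a share f of the reported standard group is below range, the reported count is 1/(1 − f) times the true one. At f = 5%, 10% and 20% that is an excess of 5.3%, 11.1% and 25% over the true count, leaving aside children with high oral doses only.

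**The case against.** Five points can be made for the SAP as it stands.

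- **The allocation is inferred.** A reader might infer that the SAP directs below-range doses to be reported as standard. It does not say so. Taking Normal from the formulary could instead leave such doses unclassified. This stands. But the children would then drop out of Table 2A-2 and [3B] without a rule, which also needs fixing.
- **[3B] may use a different variable.** A reader might infer that the [2A] grouping carries over and that the normal-dose group is the reference. The documents do not support that: the labels differ, Table 3B-1 is worded as a majority and by route, and no reference is named. This stands, so the [3B] part is only apparent. The mismatch itself needs reconciling.
- **Low doses are not invisible.** Tables 2B-1 and 2G-1 show daily dose per kg, so it would be wrong to say that the evaluation cannot show low doses at all. This stands. But per-drug summaries neither count children nor link dose to outcome, so they answer neither 2A nor [3B].
- **The bias is hypothetical and could be small.** The odds ratios of 0.82 and 0.70 need a tripled failure risk in 10% to 20% of the comparator. A child with one high IV dose and other below-range doses counts as augmented, so low doses can fall on both sides. [3B] is an unadjusted overview in a descriptive study. For scale, assume 500 cases (the SAP's accrual estimate for all cases) split 250/250 with 5% failure, that is 12.5 failures per group. The standard error of the log OR is √[2 × (1/12.5 + 1/237.5)] = 0.41, and the 95% CI around 1 is about 0.45 to 2.2. All three shifts lie inside it. This stands as to size. It does not touch the [2A] count, which is a matter of definition.
- **The fix needs data that may be incomplete.** The Data Collection list names neither dose nor weight, and a formulary range may not exist for every drug. Both must be collected for the dose-per-kg summaries in [2B], but the second limit is real and the fix should allow for it.

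**Conclusion.** The point holds in a limited form. Every dose variable in the SAP has two levels, none provides for a dose below the formulary range, and under [2A] a child with such a dose and no high IV dose is standard by complement. The count for sub-objective 2A can therefore be overstated, by an amount that equals the below-range share of the reported group and is not known in advance.

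For [3B], the supportable statement is that below-range children apparently fall in the comparator, and that the comparator is labelled differently in text and table and not named as reference. Whether the odds ratio is biased, and by how much, depends on a share and a failure risk that the SAP does not give. The 0.95 to 0.70 range is an illustration under assumed inputs with a true odds ratio of 1. A reader might infer from it that [3B] will show high dosing as protective; the documents do not establish that. The change is worth making because it is cheap and makes the 2A count match its objective.

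**What to change.** 1. Using the daily dose per kg already to be summarised and the same formulary, class each recorded dose as below range, within range or high, where the formulary gives a range. Report the number that cannot be classed.
2. In Table 2A-2, report children within range throughout, high at least once, below range at least once, and both high and below range.
3. Reconcile the dose definition across Study Outcomes, [2A], [3B] and Tables 2A-2 and 3B-1: IV only or both routes, at-least-once or majority, and one set of labels.
4. In [3B], name the reference level and show below-range children as their own row.

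The cost is SAP wording, one derived category and formulary look-up by drug and route. The downside is a slightly smaller reference group and an extra [3B] row that may hold few failures and give an imprecise odds ratio. The change governs how recorded doses are counted and takes no view on which dose is right.
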